11.235 In the absence of progression as defined by 1, 2, 3, or 4 above, the presence of a  $\geq 2 \text{ g/dl}$  decrease in HGB, or  $\geq 50\%$  decrease in platelet count, or absolute neutrophil count will NOT exclude a patient from continuing the study. Work-up of such decreases to exclude autoimmune hemolytic anemia, pure red cell aplasia, or idiopathic thrombocytopenic purpura (ITP) should be considered. However, if it is confirmed that  $\geq 2 \text{ g/dl}$  decrease in HGB, or  $\geq 50\%$  decrease in platelet count is due to CLL progression in marrow, this is considered as confirmed CLL PD.

11.236 In the case where progression is confirmed on at least 2 occasions at least 4 weeks apart, the objective status will be entered as unconfirmed progression (uPD) on the measurement form at the time this criteria is first met. Once this criteria is confirmed at least 4 weeks later, the objective status will be entered as PD. If confirmed, the date of first evidence of progression (date of first uPD) will be considered the progression date (and should be entered on the event monitoring form).

11.237 Patients whose only evidence of disease recurrence is by sensitive evaluation of MRD will NOT be considered PD.

11.24 **STABLE DISEASE (SD):** Patients who do not meet criteria for CR, CRi, nPR, CCR, PR, or PD will be classified as having "stable disease". The first formal response evaluation should occur no sooner than the end of cycle 3.

11.25 **Not PD:** The patient was evaluated for progression only this cycle and a formal response evaluation did not occur. The patient did not meet the criteria for progression per section 11.23.

Note: Formal response evaluation should occur at 3, 6, and 12 months with the first response evaluation occurring at the end of cycle 4 or at the end of the cycle closest to 3 months of therapy, whichever occurred earlier. For patients who have received more than 2 cycles of treatment and off therapy due to AE, they should have formal response evaluation between 2-8 weeks from the last therapy as long as they do not have evidence of PD. Objective status should be classified as PD vs. Not PD on cycles when a formal response evaluation does not occur.

11.3 EVALUATION OF MINIMAL RESIDUAL DISEASE (MRD): An important aspect of this trial is evaluation of minimal residual disease using a sensitive flow cytometry method capable of detecting approximately 1 CLL cell per 10,000 leukocytes following induction.

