11.544 If patient is being assessed by part a as specified in section 11.5: Lesions should be PET positive if observed in a typical FDG-avid lymphoma or the lesion was PET positive before therapy unless the lesion is too small to be detected with current PET systems ( $< 1.5$  cm in its long axis by CT).

11.545 Transformation to a more aggressive histology

11.546 In the case where progression is confirmed on at least 2 occasions at least 4 weeks apart, the objective status will be entered as unconfirmed progression (uPD) on the measurement form at the time this criterion is first met. Once this criterion is confirmed at least 4 weeks later, the objective status will be entered as PD. If confirmed, the date of first evidence of progression (date of first uPD) will be considered the progression date (and should be entered on the event monitoring form).

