- An unacceptable adverse event that occurs after the patient received at least 2 cycles of treatment, which in the opinion of the Investigator, precludes further trial participation.

13.5 Event Monitoring: Patients will enter event monitoring for the following reasons:

- If the patient develops evidence of PMD/PD (For CLL Arm A and C: PMD/PD on combination therapy; For B-NHL Arm B: PD on MK-3475 single therapy) during treatment or OBSERVATION by examination, blood counts, or imaging as defined in Sections 11.23, 11.4, 11.54 and 11.61, they will be considered to have progressed and will enter EVENT MONITORING. Refer to Section 4.0 for required tests at PMD/PD.

NOTE: Patients whose only evidence of disease recurrence is by sensitive evaluation of MRD will continue under OBSERVATION in accord with standard clinical practice and will NOT be considered PD.

- Subsequent treatment for CLL or NHL
- Failure to return for an evaluation during OBSERVATION
- Patient refusal of further study treatment or noncompliance
- Patient develops an intercurrent illness that precludes further participation, or requires a prohibited concomitant treatment
- The Investigator withdraws the patient in the patient's best interests
- Administrative reasons (e.g., the patient is transferred to hospice care)
- Pregnancy
- An unacceptable adverse event that occurs during cycles 1-2

**Note:** When a subject discontinues treatment, all applicable activities scheduled for the final trial visit should be performed at the time of discontinuation. Any adverse events which are present at the time of discontinuation/withdrawal should be followed in accordance with the safety requirements outlined in Section 10.0 -Assessing and Recording Adverse Events

13.6 A patient is deemed ineligible if after registration, it is determined that at the time of registration, the patient did not satisfy each and every eligibility criteria for study entry. The patient will go directly to the event-monitoring phase of the study:

- If the patient received treatment, all data up until the point of confirmation of ineligibility must be submitted. Event monitoring will be required per Section 18.0 of the protocol.
- If the patient never received treatment, on-study material and the End of Active Treatment/Cancel Notification Form must be submitted. No further data submission is necessary.

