16.3 Analysis Plan (to be evaluated in each arm independently)

16.31 Primary Outcome Analyses:

16.311 Definition: The primary endpoint of this trial is the proportion of patients who achieve a confirmed response to single-agent MK-3475. A confirmed response is defined to be a PR, nPR, CCR, CRi or CR (Arms A and B) or PMR, CMR, PR or CR (Arm C) noted as the objective status at any time while on single-agent MK-3475. All patients meeting the eligibility criteria who have signed a consent form and have begun treatment will be evaluable for response, with the exception of patients determined to be a major violation. For CLL patients with Richter's transformation, confirmed response is determined by response criteria defined for Richter's transformation.

16.312 Estimation: In each arm, the proportion of successes will be estimated by the number of successes divided by the total number of evaluable patients in that arm. Exact binomial confidence intervals for the true success proportion will be calculated. In addition, the confirmed response rate for all Richter's transformation patients (9 patients from Arm A and all patients in Arm C) will be calculated.

16.32 Secondary Outcome Analyses (to be evaluated in each arm independently; Arm C analyses may include the 9 Richter's transformation patients from Arm A): (For all outcomes associated with combination therapy in Arms A and C, disease measurements obtained after the last cycle of single-agent therapy are set as the baseline measurements for combination therapy).

16.321 Progression-free survival (PFS) for single-agent MK-3475 is defined as

the time from registration to the earliest date of documentation of disease progression while on single-agent MK-3475 or death due to any cause. In Arm A and Arm C, patients who initiate combination therapy for stable disease after 3 months of single-agent MK-3475 will be censored on the date that combination therapy is initiated.

In Arm A and Arm C, PFS for the combination of MK-3475 and the signal inhibitor is defined as the time from initiation of treatment with the combination therapy to the earliest date of documentation of disease progression while on combination therapy or death due to any cause.

The distribution of progression-free survival will be estimated using the method of Kaplan-Meier.

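### PFS has no rule for an unconfirmed progression (uPD) that is acted on before the 4-week confirmation; read literally, it is censored or ignored, which biases PFS upward

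*Combined protocol and SAP*

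**What the plan says.** **Confirmation.** In Arm A, the nodal, liver/spleen and lymphocyte criteria (11.231, 11.232, 11.234) require the change to be present on two occasions four weeks apart. The first occurrence is entered as uPD. Under 11.236, "Once this criteria is confirmed at least 4 weeks later, the objective status will be entered as PD", and the date is carried back conditionally: "If confirmed, the date of first evidence of progression (date of first uPD) will be considered the progression date". For Arm B, 11.546 repeats the rule: "Once this criterion is confirmed at least 4 weeks later, the objective status will be entered as PD". It also stands in 11.4 note 6, note 2 to the 11.5 table, and note 1 to the Waldenström table in 11.71.

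**Residual category.** Section 11.24 classes as stable disease every Arm A patient who meets neither a response category nor PD.

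**Change of treatment.** Sections 7.3 and 13.1 let a signal inhibitor be added in Arms A and C for progressive disease that is not flare, or for stable disease at month 3. They do not say whether uPD is progressive disease. Note 19 to the 4.1 schedule makes the progression visit the baseline for combination therapy. Section 13.5 moves patients to event monitoring for, among other reasons, "Subsequent treatment for CLL or NHL".

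**Analysis.** Single-agent PFS in 16.321 is "the time from registration to the earliest date of documentation of disease progression while on single-agent MK-3475 or death due to any cause". Its one explicit censoring rule is that, in Arms A and C, "patients who initiate combination therapy for stable disease after 3 months of single-agent MK-3475 will be censored" on the date the combination starts. Combination PFS runs "to the earliest date of documentation of disease progression while on combination therapy or death due to any cause". Duration of response (16.325) ends when relapse is documented. TFS and TNT (16.322, 16.323) count subsequent treatment, including the switch to combination, as an event.

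**The concern.** A confirmation requirement is a sensible guard against tumor flare under a checkpoint inhibitor. It works if the second assessment takes place on unchanged treatment. The plan does not say what happens when it does not.

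These patients leave the PFS risk set because they appear to be progressing. If they are censored at that point, the censoring is related to the outcome, the Kaplan-Meier assumption fails, and PFS is estimated too high. The same patient can have a TFS and TNT event at the switch and no PFS event. What is at stake is the PFS and duration-of-response description of a single agent in two small arms, where reclassifying a few patients moves the curve visibly.

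**Working it through.** **1. Can confirmation fall before treatment changes?** Cycles are 21 days, with a visit window of -2 to +7 days (4.1, note 1). After an on-time visit:

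- next visit: 21 - 2 = 19 to 21 + 7 = 28 days
- second visit: 42 - 2 = 40 to 42 + 7 = 49 days

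The next visit reaches four weeks only at the edge of its window, so confirmation usually waits about six weeks or needs an extra visit. In Arm B, nodal measurements come from imaging (11.5). Section 4.1 schedules scans at 3, 6 and 12 months and at progression, with none set about four weeks after a first progression.

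**2. What do the rules give, taken together?**

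| Patient | Status under Section 11 | Single-agent PFS under 16.321 |
|---|---|---|
| Arm A, non-Richter's, uPD at month 3, inhibitor added | Not PD, so stable disease (11.24) | Censored at the switch |
| Arm B, uPD, other lymphoma therapy starts | Not PD | Not counted; no rule says whether to censor or follow to death |
| Either arm, leaves without new therapy | uPD, may be confirmed later | Later confirmation is back-dated to the uPD |

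In the first row, the next assessment is on combination therapy against a new baseline, so it cannot confirm progression on the single agent. In the second, the 18.1 follow-up table tracks patients at six-month intervals only until progression or subsequent treatment, so confirmation is no longer sought once new therapy starts.

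**3. Size.** The plan states no PFS median, event count or power, so there is no figure to reproduce. Assume a constant hazard λ, a true median of 6 months, and a share f of *all* PFS events (deaths included) lost by censoring at the uPD. The remaining event hazard is (1 - f)λ, so

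apparent PFS(t) = [true PFS(t)]^(1 - f), and apparent median = 6/(1 - f).

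| f (assumed) | 6-month PFS (true 50%) | 12-month PFS (true 25%) | Median (true 6 months) |
|---|---|---|---|
| 10% | 0.50^0.90 = 53.6% | 0.25^0.90 = 28.7% | 6.7 months |
| 25% | 0.50^0.75 = 59.5% | 0.25^0.75 = 35.4% | 8.0 months |
| 50% | 0.50^0.50 = 70.7% | 0.25^0.50 = 50.0% | 12.0 months |

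If all 23 patients in an arm had an event, f = 10% would be 0.10 × 23 = 2.3 patients. The upper end is demanding in Arm A. Section 16.23 reports 9 Richter's patients there. If all 9 are among the 23 and their PFS follows the Richter's criteria, 23 - 9 = 14 patients remain, and f = 50% would need 11.5 of those 14 events to be lost.

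**4. If the patient is followed to death instead of censored.** Suppose the median time from uPD to death is also 6 months (assumption). Then apparent PFS(t) = e^(-λt)(1 + fλt). At f = 50%:

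- 6 months: 0.50 × (1 + 0.5 × 0.693) = 67%
- 12 months: 0.25 × (1 + 0.5 × 1.386) = 42%

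The bias is still upward, but smaller than the 71% and 50% under censoring.

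**The case against.** The strongest reply is that 16.321 speaks of documented progression and neither names nor excludes uPD. A statistician could count an acted-on uPD as documented, and the bias would then be zero. It can also be said that uPD is its own entry on the form, so 11.24 need not turn it into stable disease. Both readings are possible, but the first conflicts with the conditional back-dating in 11.236, and the second leaves the patient under no rule at all. The plan has to choose.

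Other points stand and limit the finding:

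- **Not every progression needs confirmation.** A reader might infer that it does. Transformation, cytopenia shown to be CLL marrow progression, new marrow involvement in Arm B and, as the 11.71 table reads, Waldenström clinical findings do not. Nor do Richter's patients under 11.6 and 11.61. (The note opening Section 11 points Arm A Richter's patients to 11.5; the title of 11.6 names them, and I take 11.6 as governing.)
- **Leaving is not the same as never progressing.** Without new therapy, follow-up continues and a later confirmation is back-dated. Death always counts in PFS.
- **An early switch is less clear than a month-3 switch.** Before month 3, 7.3 allows the inhibitor only for progressive disease. Either the investigator has declared progression, or the switch does not fit 7.3. The month-3 patient is the clean case.
- **Following to death need not make the bias larger.** In this model it does so only if median survival after uPD exceeds 6/(1 - f), that is 6.7, 8 or 12 months for f = 10%, 25% or 50%. The documents give no such figure.
- **TFS and TNT already capture the switch**, and PFS is a secondary, single-arm estimate with no threshold attached.

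**Conclusion.** The concern holds in a limited form. For the nodal, liver/spleen and lymphocyte criteria in non-Richter's Arm A, and the nodal, lesion and IgM criteria in Arm B, a uPD overtaken by new therapy cannot be confirmed on single-agent treatment. Taken literally, the plan then censors or ignores it in single-agent PFS, and leaves it out of duration of response in the same way. The direction is upward. The size depends on f, which the documents do not give: about 54% to 71% in place of a true 6-month PFS of 50% as f runs from 10% to 50%, under a constant hazard and censoring at the uPD.

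A reader might go further and conclude that these events are certainly deleted, or that the trial's main conclusion is affected. The documents support neither. The wording permits more than one reading, and the decision rules (5 or more responses in 23 patients for Arms A and B, and in 17 for Arm C) do not use PFS.

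**What to change.** Change 16.321 and 16.325 only. The Section 11 definitions, which also drive treatment decisions, can stay as they are.

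- Count a uPD as a progression (or relapse) event on the uPD date if, before any confirming assessment, a signal inhibitor or other anti-CLL or lymphoma therapy starts, or the patient withdraws and has no later assessment.
- Treat a uPD as no event if it is re-assessed at least four weeks later on unchanged treatment and no longer meets the criteria.
- State that the stable-disease censoring rule does not apply to patients switched at uPD.
- Word the rule to cover combination PFS too, where other therapy can likewise start before confirmation.
- Report a sensitivity analysis that censors the unconfirmed cases, with the number of patients reclassified in each arm.

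Death before confirmation is already a PFS event and needs no new rule.

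Separately, the sponsor should reconcile 7.3 and 13.1 with 11.236 on whether uPD is progressive disease, and 11.4 note 6, which limits the uPD entry to nodal progression, with the general wording of 11.236.

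The cost is a few sentences and one extra analysis, since uPD is already entered on the measurement form. The downside is that an occasional flare acted on early will count as progression and shorten PFS slightly; the sensitivity analysis shows how much depends on this choice.

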## 11.4 Summary Definition of objective response for patients with B-CLL/SLL

	CCR 	CR 	CRi 	nPR 	PR 	PD 
Physical Exam						
Nodes 	None	None	None	None	≥50% ↓	≥50% ↑, new nodes
Liver/spleen 	Not palpable	Not palpable	Not palpable	Not palpable	≥50% ↓	≥50% ↑, newly palpable
Symptoms	None	None	None	None	N/A	N/A
PERIPHERAL BLOOD						
ANC	>1500/µL	>1500/µL	See footnote 3	>1500/µL or >50% improvement from baseline	>1500/µL or >50% improvement from baseline	See footnote 6
Platelets	>100,000/µL	>100,000/µL	See footnote 3	>100,000/µL or >50% improvement from baseline	>100,000/µL or >50% improvement from baseline	Decrease of ≥ 50% from baseline secondary to CLL See footnote 6
Hemoglobin	>11.0 g/dL without transfusion	>11.0 g/dL without transfusion	See footnote 3	>11.0 g/dL or >50% improvement from baseline without transfusion	>11.0 g/dL or >50% improvement from baseline without transfusion	Decrease ≥ 2g/dL from baseline secondary to CLL See footnote 6
Lymphocytes	<4000/µL	<4000/µL	<4000/µL	<4000/µL	≥50% ↓	≥50% ↑ to at least 5,000/µL due to clear progression, not other reasons
BONE MARROW	N/A	Normocellular  ; <30% lymphocytes; no nodules	<30% lymphocytes; no nodules	<30% lymphocytes; bone marrow nodules 	N/A	N/A

1. Clinical complete response (CCR) requires fulfillment of all physical exam and peripheral blood criteria as noted in the table above. No bone marrow biopsy is required to call a patient a CCR; however, patients should have a bone marrow around the same time of the formal response evaluation as instructed in the test schedule to confirm CR.
2. Complete response (CR) requires fulfillment of all physical exam and peripheral blood criteria for a duration of  $\geq 2$  months. A bone marrow aspirate and biopsy are required to document the response as a complete within one month of the formal response evaluation where clinical and laboratory evidence of complete response was first seen (see Section 11.21).
3. Patients who fulfill all criteria for a CR but who have a persistent anemia, thrombocytopenia, or neutropenia related to drug toxicity rather than residual CLL or have hypocellular marrow will be classified as CR with incomplete marrow recovery (CRI).
4. Nodular partial response (nPR) is essentially a patient in who it appeared that CR had been obtained but nodules are present in the bone marrow. It requires fulfillment of all physical exam and lymphocyte criteria for CR; however, when the bone marrow is done to confirm CR, nodules of malignant lymphocytes are found. Patients must fulfill one or more of the blood count parameters (ANC, Platelets, Hemoglobin) but are not required to meet all 3 of these conditions. See Section 11.215 regarding the distinction between clonal and regenerative nodules.
5. Partial response (PR) requires fulfillment of at least two of the above-noted decrease in circulating lymphocytes, regression in adenopathy and regression in hepatosplenomegaly, and at least one other parameter listed above for a duration of  $\geq 2$  months. See Section 11.22.
6. Progression: Fulfilling the criteria as noted in section 11.23. Prior to the formal response evaluation, baseline on study measurements will be used to determine disease progression (e.g. not cycle by cycle comparisons). Once patients undergo formal response evaluation, the nadir value at either baseline or time of response will be used for evaluating future disease progression. In the absence of other indices of clinical progression, the presence of a  $\geq 2$  g/dL decrease in hemoglobin or a  $\geq 50\%$  decrease in platelet count and/or absolute neutrophil count will not exclude a patient from continuing on the study. Although not mandatory, bone marrow aspirate and biopsy are strongly encouraged to better define the cause of the suppressed counts (i.e. treatment- versus disease-related). In case worse cytopenia is secondary to CLL marrow progression, this is confirmed PD. In the case where progression due to nodal progression is confirmed on at least 2 occasions at least 4 weeks apart, the objective status will be entered as unconfirmed progression (uPD) on the measurement form at the time this criteria is first met. Once this criteria is confirmed at least 4 weeks later, the objective status will be entered as PD. If confirmed, the date of first evidence of progression (date of first uPD) will be considered the progression date (and should be entered on the event monitoring form).
7. Measurement of lymphadenopathy will be determined on physical exam by adding the sum of the products of the maximal perpendicular diameters of measured lesion(s). No simultaneous increase in the size of any lesions or the appearance of any new lesions may occur for more than 2 consecutive cycles. Minor fluctuations are acceptable as long as they don't exceed 50% of previous measurement. However, if they do exceed 50% of the previous measurement it should be held for 2 consecutive cycles to rule out the possibility of nodes that wax and wane. For purposes of determining CCR and nPR, all nodes on physical exam need to be  $\leq 1.5$  cm in maximal dimension or documented to be free of CLL by biopsy. NOTE: Information from CT scans regarding lymphadenopathy is not considered in the standard classification of response with the exception of the patients fitting criteria of section 11.218 and 11.228.
8. Measurement of hepatosplenomegaly will be determined by noting the maximal distance below the respective costal margins of palpable hepatosplenomegaly during rest (e.g., not during deep inspiration). NOTE: Information from CT scans regarding hepatosplenomegaly is not considered in the standard classification of response with the exception of the patients fitting criteria of section 11.218 and 11.228.

Note : See Section 11.7 for patients on Arm B with Waldenstrom macroglobulinemia

11.5 Arm B: Low grade NHL patients

Response Considerations

Definitions for clinical response for patients with lymphoma are from the Cheson et al. Revised Response Criteria for Malignant Lymphoma (Cheson, Pfistner et al. 2007). Lymph node measurements should be taken from the CT portion of the PET/CT, or MRI scans, or dedicated CT scans where applicable. Measurement of lymphadenopathy will be determined by adding the sum of the products of the maximal perpendicular diameters of measured lesions (SPD). Measurable extranodal disease should be assessed in a manner similar to that for nodal disease. For these recommendations, the spleen is considered nodal disease. Disease that is only assessable (eg, pleural effusions, bone lesions) will be recorded as present or absent only, unless, while an abnormality is still noted by imaging studies or physical examination, it is found to be histologically and pathologically negative. Disease assessable by physical exam only (e.g. skin lymphoma) will be recorded as either measurable diseases using targeted lesions or photography at the baseline and subsequent visits for response assessment.

Response is based on CT alone or the CT component of PET/CT or MRI where applicable and the PET.

PET/CT scans are required at baseline for all Follicular lymphoma grade 3

**Follicular lymphoma grade 3** PET scans are required at response assessments for these patients. These patients should be followed by the FDG-avid or PET positive criteria (part a).

**Follicular lymphoma grade 1 or 2 and marginal zone lymphoma:** Response will be determined by CT (PET/CT or dedicated CT). These patients should be followed by the variably FDG-avid or PET negative criteria (part b).

**Waldenstrom macroglobulinemia:** For patients with Waldenstrom macroglobulinemia, response will be assessed according to Section 11.6.

